10.3 Sample Size

One-hundred forty-two (142) ITT subjects (study eyes) per treatment group yields 90% power to reject H_{01} in favor of H_{A1} and conclude superiority of CyclASol over vehicle in the mean change from baseline corneal fluorescein staining (NEI scale) total score at Day 29 assuming a true difference (CyclASol minus vehicle) of -0.85, a common standard deviation of 2.2, and a two-sided alpha = 0.05. Additionally, 142 ITT subjects per treatment group yields 82% power to reject H_{02} in favor of H_{A2} and conclude superiority of CyclASol over vehicle in the mean change from baseline total OSDI score at Day 29 assuming a true difference (CyclASol minus vehicle) of -5.0, a common standard deviation of 14.5, and a two-sided alpha = 0.05. Accounting for subject discontinuations, 316 total subjects will be enrolled

For justification of clinical relevance of selected differences see Section 6.1.4.

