10.4.3 Missing Data

The primary analysis will use the FAS with available data per subject. Additional robustness analyses will include repeating the primary analysis on the PPS; the FAS imputing missing data using LOCF; the FAS imputing missing data using Markov Chain Monte Carlo (MCMC) multiple imputation methodology under different assumptions of missingness (at random and not at random); and an analysis of trimmed means (Permutt et al., 2017).

No secondary efficacy endpoints or safety endpoints will be imputed.

10.4.4 Multiplicity Considerations

Fixed sequence testing will be employed to maintain the type I error rate. The primary analyses will first test the difference in the mean change from baseline corneal fluorescein staining (NEI scale) total score between treatments at Day 29. If the test of the difference is statistically significant at the two-sided alpha = 0.05 level in favor of CyclASol, then the study will be considered a success; CyclASol will be declared to be superior to vehicle in the mean change from baseline corneal fluorescein staining (NEI scale) total score at Day 29; and the difference in the mean change from baseline total OSDI score between treatments at Day 29 will be tested at the two-sided alpha = 0.05 level.

If in addition to a statistically significant test of the difference in the mean change from baseline corneal fluorescein staining (NEI scale) total score at Day 29 in favor of CyclASol, the test of the difference in the mean change from baseline total OSDI score at Day 29 is also statistically significant in favor of CyclASol, then CyclASol will be declared to be superior to vehicle in both the mean change from baseline corneal fluorescein staining (NEI scale) total score and the mean change from baseline total OSDI score at Day 29.

[figure not shown]

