10.4.5 Primary Efficacy Analyses

The primary comparisons in this study will be between CyclASol versus vehicle at Day 29. The primary efficacy endpoints (e.g. change from baseline in corneal fluorescein staining [total NEI] and OSDI) will be analyzed separately using an ANCOVA model with terms for baseline value, treatment, and the interaction of treatment by baseline value (the interaction term will be maintained in the model only if the p-value for the term is <0.10).

Least squares mean for each treatment group and for the difference between treatment groups will be presented from the model together with two-sided p-values and 95% confidence intervals. In the event that the interaction of treatment by baseline value is significant, estimate and contrast statements will be used to determine the treatment group means and differences at the 25th, 50th, and 75th percentile of the baseline score over treatment groups.

Two-sample t-tests and Wilcoxon rank sum tests comparing treatment groups will be performed as sensitivity analyses. A mixed-effect repeated measures model will also be used as an additional sensitivity analysis of mean scores and mean changes from baseline at each visit. This model will include treatment, visit, and the interaction between treatment and visit as fixed effects, and subject as a random effect. An unstructured covariance matrix will initially be used to model the covariance among repeated measures; however, if the model fails to converge using this covariance structure, either heterogeneous TOEPLITZ, homogeneous TOEPLITZ, or CS (compound symmetry) will be implemented according to the Akaike information criterion with a correction for finite sample sizes (AICc). As an additional sensitivity analysis, a mixed-effect repeated measures model will be used with the covariance matrix selected from unstructured, heterogeneous TOEPLITZ, homogeneous TOEPLITZ and CS according to AICc.

10.4.8 Safety Variables

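### The MMRM sensitivity model omits the baseline value that the primary ANCOVA adjusts for; adding it would sharpen the comparison with the primary result at no cost

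*Combined protocol and SAP*

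**What the plan says.** Under Section 10.4.5 the two primary endpoints "will be analyzed separately using an ANCOVA model with terms for baseline value, treatment, and the interaction of treatment by baseline value", with the proviso that "the interaction term will be maintained in the model only if the p-value for the term is <0.10". If the interaction stays, results are given as "means and differences at the 25th, 50th, and 75th percentile of the baseline score over treatment groups".

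The same section then plans an MMRM as an "additional sensitivity analysis of mean scores and mean changes from baseline at each visit". Its terms are listed in full: "This model will include treatment, visit, and the interaction between treatment and visit as fixed effects, and subject as a random effect". Baseline is not among them. A second version, in which "a mixed-effect repeated measures model will be used with the covariance matrix selected from unstructured, heterogeneous TOEPLITZ, homogeneous TOEPLITZ and CS according to AICc", changes how the covariance structure is chosen and adds no covariate. The synopsis names the repeated measures analysis without giving terms. No visible passage supplies a baseline term; Sections 10.4.6 and 10.4.7 do not appear in the public copy.

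Section 10.4.3 bases the primary analysis on available data in the FAS. It repeats that analysis on the PPS, with LOCF, and under multiple imputation assuming data missing at random and not at random.

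**The concern.** An MMRM set beside an available-data ANCOVA can show whether using the Day 15 values of subjects with no Day 29 value changes the answer. For that comparison to be clean, the two models should differ in how they handle missing data and not in their covariates. Here they differ in both. A gap between them could be read as a missing-data signal when it is only chance baseline imbalance, which the planned two-sample t-test already shows.

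There is also a conditional validity point. Leaving out a variable that predicts both dropout and outcome can bias a likelihood-based analysis if the dropout pattern differs between arms. Finally, the model is to be fitted to scores and to changes. Without baseline, these two fits give different Day 29 contrasts, and the text does not say which one counts.

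**Working it through.** **The plan's own figures.** Section 10.3 gives 142 per arm, a staining difference of -0.85 with SD 2.2, and an OSDI difference of -5.0 with "a common standard deviation of 14.5". With sqrt(2/142) = 0.1187:

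- Staining SE = 2.2 x 0.1187 = 0.261; 0.85/0.261 - 1.96 = 1.30, so power is 90.2% (stated: 90%).
- OSDI SE = 14.5 x 0.1187 = 1.72; 5.0/1.72 - 1.96 = 0.95, so power is 82.8% (stated: 82%).
- 142/0.90 = 157.8, rounded up to 158 per arm and 316 in total (stated: 316, with 10% dropout in the synopsis).

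The figures reproduce, and they are for unadjusted comparisons.

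**Precision.** Let r be the correlation of change with baseline (assumed; not in the documents). Adjusting for baseline multiplies the SE by sqrt(1 - r^2), so omitting it inflates the SE by 1/sqrt(1 - r^2).

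**Departure from the ANCOVA.** With complete data its SD is 2.2 x |r| x 0.1187, which is 0.05, 0.08, 0.10 and 0.13 points at r = -0.2, -0.3, -0.4 and -0.5. A simulation adds missing data. It uses 158 per arm, SD of change 2.2, true difference -0.85, and 10% missing completely at random at Day 29, half of these with a Day 15 value. The Day 15 to Day 29 residual correlation is 0.5 (assumed) and the covariance unstructured.

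| r | SE with baseline, 142 per arm | SE inflation if omitted | SD of MMRM minus ANCOVA, no baseline | Same, with baseline | Fall in variance on adding baseline |
|---|---|---|---|---|---|
| 0 | 0.261 | 0% | 0.034 | 0.030 | 22% |
| -0.2 | 0.256 | 2% | 0.062 | 0.029 | 78% |
| -0.3 | 0.249 | 5% | 0.083 | 0.029 | 88% |
| -0.4 | 0.239 | 9% | 0.109 | 0.028 | 93% |
| -0.5 | 0.226 | 15% | 0.132 | 0.026 | 96% |

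The last column is 1 minus the squared ratio of the two SDs. At r = -0.3, -0.4 and -0.5, the t-test departs from the ANCOVA by an SD of 0.079, 0.107 and 0.130, almost the same as the unadjusted MMRM. Given a significant ANCOVA, the MMRM is non-significant in 3.3%, 5.0% and 6.8% of trials without baseline, against 0.5%, 0.3% and 0.3% with it.

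For OSDI with complete data, the SE is 1.72 without baseline and 1.64, 1.58 and 1.49 with it at the same three correlations. The SD of the departure (14.5 x |r| x 0.1187) is 0.52, 0.69 and 0.86 points.

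**Bias.** The set-up is the same but with no true effect. Dropout is logistic in standardized baseline at an assumed odds ratio of 2.7 per SD, and r runs from -0.3 to -0.5. Bias of the unadjusted change fit, in staining points:

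- Dropout unrelated to baseline, or related identically in both arms at equal rates: about 0.
- Dependence in one arm only: 0.04 to 0.07.
- Same dependence in both arms, but 5% dropout against 15%: about 0.04 to 0.06.
- Dependence in opposite directions: 0.08 to 0.14.

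The sign depends on which arm loses the high-baseline subjects. The ANCOVA and the baseline-adjusted MMRM stay at about 0 throughout. As a stress case, opposite-direction dependence at log-odds 1.1 per SD, with no dropout contributing a Day 15 value and a baseline to follow-up correlation of 0.3, gives 0.25, just under one SE.

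**Scores against changes.** The two unadjusted contrasts differ by the baseline imbalance, whose SD is 0.12 points per point of baseline SD. The score's slope on baseline is 1 + r x 2.2/SD(baseline). At r = -0.5 it is 0.45 if the baseline SD is 2.0 and -0.10 if it is 1.0, so the size and sign of any score-fit bias depend on a baseline SD that the documents do not give. If Day 1 is modelled as a response in the score fit, the bias falls to within 0.008, but the departure from the ANCOVA remains (SD 0.080 to 0.127).

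With baseline and baseline-by-visit in the model, the score and change contrasts are identical.

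**The case against.** The strongest reply is that little depends on this model. It is one of several sensitivity analyses, and Section 10.4.3 already repeats the baseline-adjusted analysis on the PPS, with LOCF and under multiple imputation. The plan never says that the MMRM is there to recover Day 15 information; it describes an analysis at each visit, beside t and Wilcoxon tests that are unadjusted by design. All of that stands and is why the point is minor.

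The reply is also right that the sizes rest on assumptions. No correlation is given. Section 4.5 describes a target population with baseline staining of at least 10, which may narrow the baseline range and weaken the correlation. Nothing in the documents suggests that dropout within four weeks would depend on baseline differently by arm.

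Four stronger readings are tempting, and the documents do not support them:

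- That the MMRM is biased as planned. The bias needs a difference between arms in baseline-related dropout or in its rate.
- That nearly all disagreement with the ANCOVA would come from the missing covariate. This holds at moderate correlations but not at r = 0, where the SDs are 0.034 and 0.030.
- That the score and change fits are biased in opposite directions. This fails when the baseline SD is small and the correlation strong.
- That the lack of an MMRM counterpart to the percentile-specific ANCOVA results is a defect. The t and Wilcoxon tests have none either; carrying the interaction across is a preference.

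What survives is the omission itself: a closed list of terms, in the section that adjusts the primary model for baseline, with no reason given for leaving it out.

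**Conclusion.** The point holds as a minor one. The MMRM omits a covariate that the primary model uses, and three consequences follow:

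- **Precision.** The loss is 0% to 15% of the SE for assumed correlations from 0 to -0.5.
- **Comparability.** At correlations of -0.3 to -0.5, the MMRM departs from the ANCOVA by an SD of 0.08 to 0.13 points, against about 0.03 with baseline. A disagreement would then mostly reflect the covariate and not the handling of missing data.
- **Bias.** It arises only if baseline-related dropout, or its rate, differs by arm. At an odds ratio of 2.7 per SD it is about 0.04 to 0.14 points, against an SE of 0.26 and a planned effect of 0.85.

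The correlation, baseline SD, residual correlation and dropout mechanism are all assumed. A reader might infer that the primary conclusion or the power is at risk. It is not: success rests on the fixed-sequence ANCOVA tests, which adjust for baseline and showed no bias in these scenarios, and the primary test, alpha and sample size do not depend on the MMRM.

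**What to change.** In Section 10.4.5, and in any separate SAP, add baseline value and baseline-by-visit as fixed effects to the MMRM of change from baseline. Do this in both the first version and the AICc-selected version, and name the Day 29 treatment contrast as the sensitivity estimate. One model then serves for scores and changes.

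Two optional refinements are not part of the finding: carrying the treatment-by-baseline term into the MMRM when the ANCOVA retains it, and stating whether subject is the repeated-measures block or a separate random intercept.

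The cost is a wording change and a small programming change. Baseline is already collected, so no new data are needed.

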Dosage/Dose Regimen:	2) Vehicle Ophthalmic Solution (F4H5)					
	A 14-day study-run-in period will be used for subject selection before randomization. During this period, all subjects will receive Systane [®] Balance to dose with bilaterally BID.					

Summary of Visit Schedule:	 This clinical study involves 6 visits over the course of approximately 14 weeks: Visit 0, Day -14 ± 2 days, Screening; Visit 1, Day 1, Baseline/Randomization; Visit 2, Day 15 ± 1 days, 2-Week Follow-Up; Visit 3, Day 29 ± 2 days, 4-Week Follow-Up; Visit 4, Day 57 ± 2 days, 8-Week Follow-Up; and Visit 5, Day 85 ± 2 days, 12-Week Follow-Up and Study Exit.
Measures Taken to Reduce Bias:	and vehicle-controlled clinical study.
Study Population Characteristics:	
Number of Subjects:	Approximately subjects will be screened to enroll at least 316 (158 per treatment arm) subjects at approximately 10 sites.
Condition/Disease:	Dry Eye Disease (keratoconjunctivitis sicca)
Condition/Disease: Inclusion Criteria:	 Dry Eye Disease (keratoconjunctivitis sicca) Each subject must: a. Be at least 18 years of age; b. Provide written informed consent; c. Have a subject reported history of Dry Eye Disease ; d. Be currently using (within 30 days before Visit 0) over-the-counter (OTC) eye drops, lubricating gels and/or artificial tears for dry eye symptoms at Visit 0; e. Have an OSDI[®] score of at Visit 0 and Visit 1; f. Have a total corneal fluorescein staining score of g. Have a total lissamine green conjunctival score (sum of temporal and nasal regions) h. Have an unanesthetized Schirmer's Test score

	participate in all study assessments and visits.
Exclusion Criteria:	Each subject must not:
	 a. Have any clinically significant slit-lamp findings at Visit 0 that require prescriptive medical treatment and/or in the opinion of the investigator may interfere with study parameters including trauma, Steven Johnson Syndrome, advanced epithelial basement membrane disease;
	 c. Have abnormal lid anatomy (e.g. incomplete eyelid closure, entropion, or ectropion) or abnormal
	e. Have an ocular or periocular malignancy;
	g. Have a history of herpetic keratitis;
	h. Have active ocular allergies or ocular allergies that may become active during the study period;
	 Be diagnosed with an ongoing ocular or systemic infection (bacterial, viral, or fungal), including a fever, or be undergoing treatment with antibiotics at Visit 0 or Visit 1;

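### The repeated-measures sensitivity model, read literally, has one redundant covariance parameter, which can needlessly trigger its own fallback rule

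*Combined protocol and SAP*

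**What the plan says.** Section 10.4.5 of the combined protocol and SAP makes a Day 29 ANCOVA the primary analysis: the endpoints "will be analyzed separately using an ANCOVA model with terms for baseline value, treatment, and the interaction of treatment by baseline value". The repeated-measures model is secondary to it: "A mixed-effect repeated measures model will also be used as an additional sensitivity analysis of mean scores and mean changes from baseline at each visit".

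The model is specified in two consecutive sentences, which take treatment, visit and their interaction "as fixed effects, and subject as a random effect. An unstructured covariance matrix will initially be used to model the covariance among repeated measures". The fallback rule is that "if the model fails to converge using this covariance structure, either heterogeneous TOEPLITZ, homogeneous TOEPLITZ, or CS (compound symmetry) will be implemented", with the choice made by AICc. A second repeated-measures analysis has its "covariance matrix selected from unstructured, heterogeneous TOEPLITZ, homogeneous TOEPLITZ and CS according to AICc"; its fixed and random effects are not restated.

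The Synopsis puts the post-baseline visits at Days 15, 29, 57 and 85 (in part: "Visit 3, Day 29 ± 2 days, 4-Week Follow-Up; Visit 4, Day 57 ± 2 days, 8-Week Follow-Up"). The gaps are therefore 14, 28 and 28 days.

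**The concern.** A random subject effect and an unstructured residual matrix are two ways of describing the same within-subject dependence. The unstructured matrix leaves nothing for the subject variance to explain, so the data cannot separate the two. The plan then makes failure to converge the condition for leaving the unstructured matrix, and a redundant parameter invites numerical trouble of that kind. It may show up as non-convergence, a singular Hessian or a variance component set to zero, and the plan does not say which of these counts as failure. Two programmers could follow the text faithfully and report different models.

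The fallbacks are also more restrictive. Both Toeplitz forms give all adjacent visits one correlation although the gaps differ. Homogeneous Toeplitz and compound symmetry also assume equal variance at every visit. At stake is the clarity and calibration of one check on the primary result, a check that uses Day 15 data for subjects without a Day 29 value.

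**Working it through.** **Inputs.** Four post-baseline visits at Days 15, 29, 57 and 85 (Synopsis). SD 2.2 for change in corneal staining and 142 per arm (10.3); 158 per arm randomised (5.1). The plan gives no within-subject correlations and no visit-specific SDs, so those below are assumptions.

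**The plan's own figures.** None is stated for this model. The sample size in 10.3 reproduces. For staining, 0.85/(2.2 × √(2/142)) = 3.256 and Φ(3.256 − 1.960) = 90.2% (stated 90%). For OSDI, 5.0/(14.5 × √(2/142)) = 2.906 and Φ(2.906 − 1.960) = 82.8% (stated 82%). With 10% dropout, 142/0.9 = 157.8, so 158 per arm and 316 in total.

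**Step 1: parameter count.** Read literally, the marginal covariance is V = σ_b² J + R, where J is the 4 × 4 matrix of ones and R the residual matrix. V has 4 × 5/2 = 10 distinct elements. The rank of the Jacobian of those elements with respect to the parameters gives:

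| R | Parameters in R | With subject effect | Rank |
|---|---|---|---|
| Unstructured | 10 | 11 | 10 |
| Heterogeneous Toeplitz, visit variances differ | 7 | 8 | 8 |
| Heterogeneous Toeplitz, visit variances equal | 7 | 8 | 7 |
| Homogeneous Toeplitz | 4 | 5 | 4 |
| Compound symmetry | 2 | 3 | 2 |

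This is algebra and needs no assumption about the data. If the model for mean scores also includes baseline (five visits), the unstructured count is 16 for 15 and the conclusion is the same.

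**Step 2: what is not identified.** For a given V, any σ_b² from 0 up to 1/(1′V⁻¹1) can be absorbed by R = V − σ_b² J with the likelihood unchanged. Assume SD 2.2 at each visit and correlation exp(−days apart/θ). The upper limit is then 2.30, 3.07 or 3.75 for θ = 30, 60 or 120. Only the split of V is undetermined. V itself, the Day 29 treatment difference and its standard error equal those of the unstructured model alone.

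**Step 3: does the fit fail?** In 100 simulated datasets (284 subjects, four visits, assumed time-decay correlation) a general-purpose BFGS optimiser converged every time, with V within 0.0001 of the unstructured estimate. In 40 further datasets a ridge-stabilised Newton fit also always converged, but every Hessian was singular. Whether the fallback is triggered thus depends on the software and on how the rule is read.

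**Step 4: cost of falling back.** Toeplitz lag 1 pools gaps of 14, 28 and 28 days; lag 2 pools 42 and 56. At θ = 60 the true lag-1 correlations are 0.79, 0.63 and 0.63, and homogeneous Toeplitz fits 0.68 to all three.

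For the Day 29 test at 158 per arm, let r be the model-based SE divided by the true SE. Type I error is 2Φ(−1.96 r). Examples at θ = 120 with complete data:

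- Equal SDs: true SE = 2.2 × √(2/158) = 0.2475. Heterogeneous Toeplitz gives 0.2439, r = 0.985, error 5.35%. Homogeneous Toeplitz and compound symmetry give 0.2475, error 5.0%.
- SD rising over visits: homogeneous Toeplitz gives 0.2681 against 0.2475, r = 1.083, error 3.4%.
- SD lowest at Day 15 and highest at Day 29: homogeneous Toeplitz gives 0.2427 against 0.2700, r = 0.899, error 7.8%.

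The scenarios crossed θ of 30, 60 and 120 with these SD patterns and with no dropout, 10% by Day 85 or 10% before Day 29. Heterogeneous Toeplitz gave 5.1–5.4% throughout. With equal SDs, homogeneous Toeplitz gave 4.8–5.0% and compound symmetry 4.7–5.0%. With unequal SDs these two ranged over about 3.4–7.8%.

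**The case against.** The strongest reply is that the sponsor may mean subject only as the identifier of the repeated-measures block, with no separate random intercept. The sentence can be read that way, and on that reading the model is sound. This stands as a possible intention. The text does not say so, however, and its literal content is a random effect plus an unstructured matrix.

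A reader might also infer more than the documents support:

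- *That the Day 29 result is not estimable.* It is: only the division of V into subject and residual parts is undetermined (Step 2).
- *That the fallback will be used.* It may be. Redundancy alone did not stop convergence in Step 3.
- *That AICc selection is distorted.* If every candidate carries one redundant parameter, with n = 284 the AICc penalty 2k + 2k(k+1)/(n − k − 1) rises from 20.81 to 22.97 for unstructured (k = 10 to 11) and from 4.04 to 6.09 for compound symmetry (k = 2 to 3). The increments, 2.17 and 2.04, differ by about 0.12. Under assumed decay (correlation 0.5 or 0.3 per 28 days, with or without a constant part of 0.3), the better Toeplitz is 13–20 AIC units worse than unstructured, so the shift is negligible.
- *That unequal spacing spoils the test.* Spacing alone moves the Day 29 type I error by about 0.4 points or less. Compound symmetry uses no lags, so spacing is not the objection to it.
- *That 3.4–7.8% is the expected error.* It needs unequal visit SDs and a poor choice among the fallbacks. With SD growing from 1.8 to 2.7 (assumed), heterogeneous Toeplitz improves −2 log L by about 78–121 over homogeneous Toeplitz for three extra parameters, so AICc would choose it.

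It is also fair that the second repeated-measures analysis keeps unstructured among its candidates, and that 10.4.3 adds LOCF, multiple imputation, trimmed means and a per-protocol analysis. The primary result does not depend on this model alone for its robustness.

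**Conclusion.** The point holds as a minor error of specification. Read literally, the model has 11 covariance parameters for 10 moments, and homogeneous Toeplitz and compound symmetry share the fault. The practical risk is a needless, software-dependent move to a restricted structure under a rule that does not define failure. Under the assumed covariances, that move costs a few tenths of a point of type I error if heterogeneous Toeplitz is chosen, and up to about 3 points in either direction if homogeneous Toeplitz or compound symmetry is used with unequal visit variances.

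The rank result rests only on the literal reading. The type I figures rest on assumed correlations, SDs and dropout that the documents do not supply; they illustrate size and are not bounds. The primary ANCOVA, its alpha and the sample size are unaffected.

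**What to change.** In 10.4.5, for both repeated-measures models, remove the clause that makes subject a random effect and state that subject only defines the block within which visits are correlated. The unstructured model then has 10 parameters with rank 10 and gives the same Day 29 estimate and standard error as the redundant model at its maximum, so nothing is lost. Specify empirical (sandwich) standard errors whenever a structure other than unstructured is used.

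It would help to say what counts as convergence failure, including whether a non-positive-definite Hessian does. A time-decay structure on study day with visit-specific variances could be added as a further fallback. This is optional: sandwich errors protect the standard error but do not correct how a misfitted correlation carries Day 15 information to a missing Day 29 value.

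The cost is a few sentences of SAP wording. No extra data, visits or subjects are needed.
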